Between May, 2007, and April, 2012, a total of 1440 patients who received IV-tPA were registered in the Thrombolysis Implementation and Monitor of Acute Ischemic Stroke in China (TIMS-China). Final analysis demonstrated 2 important facts regarding IV-tPA dosages. First, the standard-dose IV-tPA treatment protocol was safe for Chinese patients with stroke, without any increased rate of symptomatic intracranial haemorrhage (sICH) according to ECASS III definition or mortality compared with the low dose group. The sICH mentioned below is all according to ECASS III definition unless other specified. Second, patients with stroke receiving standard dose IV-tPA may have more favorable outcome than those receiving low doses of IV-tPA [[P13-12586](#)].

The 2013 version of Chinese IV rt-PA consensus was published based on previous version of China guideline and all new publications on the use of IV rt-PA for AIS. The Chinese Stroke Therapy Expert Panel concluded that Intravenous rt-PA is currently the most effective therapy for acute ischemic stroke and there is clinical evidence supporting the use of IV rt-PA between 3 and 4.5 hours after the onset with several exclusion criteria. After years of stroke quality care improvement, incidence of stroke has not decreased as expected. Part of the reasons might be due to the gap between clinical guidance and real practice.

From the Chinese National Stroke Registry (CNSR), among 11675 acute ischemic stroke patients with documented acute onset time, only 189 patients finally were treated with

alteplase [[P11-07866](#)]. In the last five years, proportion of thrombolysis within early hours increased from 7% to 20%, data from the United States is around 80%, the gap is still there. As of June 2014, MOST data demonstrated periodical analysis: totally 5049 cases were reported, within which 3872 cases (77%) were administered with IV rt-PA. Of all the patients who received early IV rt-PA thrombolysis, 67% of the patients showed functional improvement measured by NIHSS score, SICH rate was 4.1%, observed death rate was 4.3% [[Other Reference](#)]. The prognosis of Chinese patients with thrombolytic therapy is better than other Asian countries, however, Europe and the United States are even better. Therefore, it is encouraged to be more active in early thrombolysis in China.

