#### **5.1.2.2 Secondary Safety Endpoints**

- Patient survival probability at visit 5 (censoring at day 90)
- Frequency of death related to stroke or of neurological causes
- Frequency and severity of adverse events
- Incidence of cerebral herniation and symptomatic edema

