## **7. STATISTICAL METHODS AND DETERMINATION OF SAMPLE SIZE**

### **7.1 STATISTICAL DESIGN - MODEL**

This is an open-label, single-arm, multi-center, Phase III trial that is designed to assess the safety and efficacy of alteplase (rt-PA) of 0.9 mg/kg rt-PA (intravenously infused over 1 hour) in acute ischemic stroke patients within 3-4.5 hrs from onset of symptoms in the Chinese population. Considering the design of single-arm study and binary nature of primary endpoints, the point estimators will be mainly presented along with the corresponding 95% confidence intervals.

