### **7.3.4 Safety analyses**

Safety analysis will be performed based on full analysis set.

Patient's survival at Day 90 (censoring at 90 days) will be analysed using the Kaplan-Meier method. The median survival along with 95% confidence interval, using Greenwood's standard error estimate, will be presented. The Kaplan-Meier estimates will also be plotted over the observation period of 90 days.

The frequency of death related to stroke or of neurological causes and the incidence of cerebral herniation and symptomatic edema will be analysed descriptively.

Adverse events will be coded using the Medical Dictionary for Regulatory Activities (MedDRA) coding dictionary. The frequency, severity and causal relationship of adverse events will be tabulated by system organ class and preferred term after coding according to MedDRA. Because this study is a single dose drug administration (duration of approximately one hour), the incidence and severity of adverse events will be displayed by treatment periods. All AEs which occurred through the single dose treatment phase and throughout the REP will be considered as on treatment. Events which occurred after the REP will be considered as post treatment. The frequency of on-treatment AEs will be summarized as primary interest. The frequency of all AEs collected until the end of the study will also be summarized. More

details will be specified in Statistical Analysis Plan. Standard BI summary tables and listings will be produced.

Vital signs, physical examinations, or other safety-relevant data observed at screening, baseline, during the course of the trial and at the end-of-trial evaluation will be assessed with regard to possible changes compared to findings before start of treatment.

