## 7.7 DETERMINATION OF SAMPLE SIZE

The study will enrol approximately 120 patients. The sample size calculation takes account into both safety and efficacy considerations.

Regarding the primary safety endpoint, an observed sICH rate of 2.4%, i.e., 3 sICH events out of 120 patients, will result in an exact binomial 95% CI (0.48%, 6.99%) with the confidence width as 6.51%, which is considered as reasonable estimation precision.

The percentage of mRS 0-1 (favourable outcome) responder at day 90 is the primary efficacy endpoint. The range of the response rate from historical review was from 40% to 60% [P05-03664]. If assuming an underlying response rate of 55% of rt-PA treatment in Chinese patients, for the planned sample size of 120 patients, a power of 91.5% can be achieved. The sample size calculations in Table 7.7.1 have been performed based on a one sample test for proportion with a two-sided significance level of 0.05 and power ranging from 80% to 90%. Calculations were performed using ADDPLAN version 6.

Table 7.7:1

Sample size calculations based on a one sample test with a two-sided significance level of 0.05 and various assumptions of percentages of mRS 0-1 responders (n=120)

Assumed mRS response rate	Number of mRS 0-1 responders	Power(%)
52.5%	63	79.4
53.3%	64	84.2
55.0%	66	91.5

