7. PLANNED ANALYSIS

Unless otherwise specified, the following general conventions for End-of-Text (EoT) [\[5\]](#) tables should be used regarding all descriptive statistical analysis and result presentations.

The set of summary statistics: N / Mean / SD / Min / Median / Max are for continuous data with one more decimal place compared to the original data in the subject data listing. For tables that are provided for endpoints with some extreme data, Q1 and Q3 would be preferred to Min and Max.

Tabulations of frequencies for categorical data will include all possible categories and will display the number of observations in a category as well as the percentage (%) (unless otherwise specified, all patients in the respective patient set whether they have non-missing values or not). Percentages will be rounded to one decimal place. The category missing will be displayed only if there are actually missing values. All the confidence interval calculations for proportions will use the Wilson score method.

The visit will be analysed as calculated visit and should be named ‘Baseline’, ‘Day0(1H)’, ‘Day0(2H)’, ‘Day1’, ‘Day7’, ‘Day30’ and ‘Day90’ as described in [Section 6.7](#). The units of variables should be given in the titles or column/row descriptors in square brackets (e.g. [mmHg]), unless the variable does not have a unit (e.g. scores). And the imputation rules for missing data will be applied as in [Section 6.6](#).

An independent data monitoring committee (DMC) will oversee the trial conduct, monitor safety data monthly, and review the interim analysis results when 60 patients complete the study. As for details please refer to DMC SAP. [\[6\]](#)

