7.5 SECONDARY ENDPOINT(S)

7.5.1 Key secondary endpoint(s)

Not applicable.

7.5.2 (Other) Secondary endpoint(s)

The secondary efficacy endpoint is the percentage of global outcome at Visit 5. A global outcome responder is defined as patient with outcomes at Visit 5 of a score of 0 or 1 on the mRS, a score of 95 or higher on the Barthel Index, a score of 0 or 1 on the NIHSS, and a

score of 1 on the Glasgow Outcome Scale. The proportion of global outcome responders will be displayed along with corresponding 95% CIs. Each item of the composite criteria global outcome responder (refer to [Section 5.2.2](#)) will be evaluated separately as well. Its observed result will also be summarized. The imputation rules described in [Section 6.6](#) will be applied for the primary analysis.

The secondary safety endpoints are:

- Patient's survival at Day 90 (censoring at 90 days)

The cumulative probability (Kaplan-Meier estimate) of death from bolus treatment administration to Day 90 will be analysed and plotted by a Kaplan-Meier survival with the median survival along with 95% confidence interval, using Greenwood's standard error estimate. The Kaplan-Meier estimates will also be analysed over the observation period of 90 days.

- Frequency of deaths related to stroke or of neurological causes will be analysed descriptively.
- Incidence of cerebral herniation and symptomatic edema will be analyzed descriptively.
- Frequency and severity of adverse events refer to [Section 7.8.1](#).

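### The 95% CI planned for the Day 90 survival endpoint is attached to median survival, which will almost certainly not be reached, so the endpoint itself has no stated CI

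*Protocol*

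**What the plan says.** Protocol 5.1.2.2 lists as the first secondary safety endpoint: "Patient survival probability at visit 5 (censoring at day 90". Protocol 7.3.4 plans a Kaplan-Meier analysis and a plot over 90 days, and the interval it specifies is for the median: "The median survival along with 95% confidence interval", with Greenwood's standard error.

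SAP 7.5.2 comes closer to the endpoint. It states that "The cumulative probability (Kaplan-Meier estimate) of death from bolus treatment administration to Day 90 will be analysed and plotted", but the same sentence again attaches the interval to the median: "with the median survival along with 95% confidence interval", also with Greenwood's standard error.

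Two general statements about intervals might be thought to fill the gap. Protocol 7.1 refers to the "binary nature of primary endpoints, the point estimators will be mainly presented along with the corresponding 95% confidence intervals". The introduction to SAP section 7 says: "All the confidence interval calculations for proportions will use the Wilson score method".

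SAP 6.6 defines survival time as the date of death (or of last contact) minus the date of the bolus, plus one. In the Day 90 analysis, any time above 90 is cut to 90 and recoded as alive. Protocol 6.3.1 and SAP 6.7 call the day of treatment D0 and allow Visit 5 from Day 83 to Day 97.

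**The concern.** The endpoint is a probability at a fixed time, whereas the planned interval is for a time at which half the patients have died. Follow-up for the endpoint stops at 90 days, so the median exists only if at least half the cohort dies in that period. Nothing in the protocol suggests mortality of that order.

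Greenwood's formula gives the standard error of the survival function S(t), so the authors may have wanted an interval for S(90). Neither document says so.

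This is a single-arm trial whose main presentation is estimates with confidence intervals. If the text is programmed as written, the Day 90 mortality figure appears without a stated interval, next to a median and limits shown as not estimable.

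**Working it through.** **Inputs.** n = 120 (Protocol 7.7). Follow-up for the endpoint is cut at 90 days (SAP 6.6). The protocol quotes one death rate for Chinese patients given early rt-PA: "observed death rate was 4.3"% (Protocol 1.1), with no follow-up time stated. Mortality of 10%, 20% and 30% is assumed here to show a range. The plan gives no precision figure for survival, so there is none to reproduce.

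**1. Can the median be reached?** With no censoring before Day 90, S(90) = 1 − d/120 for d deaths. The median needs S(90) ≤ 0.5, so d ≥ 60. Limits for the median come from inverting the 95% band of S(t):

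- The lower limit exists once the lower band is at or below 0.5. On the log-log scale the lower band is 0.5066 at 48 deaths and 0.4983 at 49. On the linear scale it is 0.5037 at 49 and 0.4951 at 50.
- The upper limit needs 71 deaths on either scale.

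Binomial probabilities with n = 120:

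| 90-day mortality | P(d ≥ 60), median | P(d ≥ 49), lower limit, log-log | P(d ≥ 50), lower limit, linear |
|---|---|---|---|
| 4.3% | 7e-49 | 7e-35 | 4e-36 |
| 10% | 2e-28 | 8.6e-19 | 1.4e-19 |
| 20% | 2e-13 | 1.5e-7 | 5.1e-8 |
| 30% | 3.5e-6 | 0.0075 | 0.0044 |

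**2. Check against the plan's own assumption.** Protocol 7.7 writes: "If assuming an underlying response rate of 55% of rt-PA treatment in Chinese patients". If 55% is observed, 0.55 × 120 = 66 patients are alive with mRS 0-1, so at most 120 − 66 = 54 have died. That is below 60, so the median could not be reached. The bound does not exclude a lower limit for the median (49 or 50 deaths); the table shows why that limit is also unlikely.

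**3. The interval that could be reported.** Without earlier censoring, Greenwood's SE reduces to √(S(1 − S)/120). The log-log limits are S^exp(±1.96·s), with s = √((1 − S)/(120·S))/|ln S|.

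| Deaths | S(90) | SE (points) | 95% CI, log-log |
|---|---|---|---|
| 6 | 95.0% | 1.99 | 89.2 to 97.7 |
| 12 | 90.0% | 2.74 | 83.1 to 94.2 |
| 18 | 85.0% | 3.26 | 77.3 to 90.3 |
| 24 | 80.0% | 3.65 | 71.7 to 86.1 |

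**4. Do the general rules cover it?** The Protocol 7.1 statement is tied to the binary primary endpoints. The Wilson rule is for proportions, and S(90) need not be one, because a survivor whose Visit 5 falls on Days 83 to 89 can be censored before Day 90. Example under the SAP's own rule: 11 deaths before Day 84, then 54 of the 108 survivors last seen on Day 84, then one death on Day 88. At Day 88, 120 − 11 − 54 = 55 are at risk, so S(90) = (109/120) × (54/55) = 0.892 (81.4 to 93.8). The simple proportion is 108/120 = 0.900.

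**5. Day count (minor).** The schedule calls the bolus day D0, but the survival formula makes it day 1. A death on Study Day 90 therefore has time 91 and is recoded as alive in the Day 90 analysis. With 12 deaths, one of them on Day 90, and 108 survivors followed past Day 90:

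- SAP rule (plus one, cut at 90): 11 events, S = 90.8% (84.1 to 94.8).
- Plus one with cut and cap at 91, or no plus one with cut at 90: 12 events, S = 90.0% (83.1 to 94.2).

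Each such death moves the estimate by 1/120 = 0.83 points. If deaths were spread evenly over the 91 days D0 to D90, the expected number on that day is 120 × mortality/91: 0.06 at 4.3% and 0.40 at 30%.

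**The case against.** The strongest objection is that the SAP sentence opens with the Kaplan-Meier probability of death to Day 90 and closes with a 95% interval from Greenwood's SE, so a sympathetic programmer would put the interval on S(90). This may well be what was meant, and the Day 90 point estimate is planned. But the interval is grammatically attached to the median in both documents, and the SAP, which exists to make the protocol precise, repeats the wording.

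Second, little is lost in practice. Both documents expect complete vital status, and a Wilson interval from the number of deaths is close to the log-log one: with 12 deaths, 83.3 to 94.2 against 83.1 to 94.2. The two estimates part only if a death follows early Visit 5 censoring, which should be rare. This limits the harm, but it leaves the reader to build the interval.

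Third, Kaplan-Meier output may be specified in the sponsor's standard table shells or in SAP text that is not public. That can be neither confirmed nor excluded.

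Fourth, the endpoint is secondary and descriptive, and no interim rule uses it. That is correct, and this is a reporting matter only. The day-count issue is smaller still: such a death stays in the overall-study survival analysis.

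**Conclusion.** The concern holds. As written, the endpoint, survival probability at Day 90, has no stated interval, and the interval that is specified belongs to a median that will almost certainly not be reached: probability at most 3.5e-6 for 90-day mortality up to 30%. Even one limit of its CI has probability below 0.01 at 30% and about 1.5e-7 or less at 20%. These figures assume complete follow-up to Day 90. The 4.3% rate has no stated follow-up time, and the 10% to 30% values are assumptions.

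The consequence is a mortality estimate reported without stated precision, when its 95% interval at 12 deaths would run from 83.1% to 94.2%. No hypothesis test, sample size or interim decision is affected. The one-day offset is a true but minor inconsistency, confined to deaths on exactly Study Day 90.

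**What to change.** In Protocol 7.3.4 and SAP 7.5.2, replace the median with the Kaplan-Meier probability of survival (or death) at Day 90 and its 95% CI from Greenwood's standard error, and name the scale, for example log-log.

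Minor, in SAP 6.6: use one day convention for both survival analyses.

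- The smaller edit keeps the plus one everywhere, moves the Day 90 cut and cap from 90 to 91, and states that survival time 91 is Study Day 90. The overall-study formulas then stay as they are, and a death on the bolus day has time 1.
- The alternative drops the plus one from the Day 90 and the overall-study formulas and makes sure that deaths at time 0 still count as events.

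In either case, the bracketed note beside the 90-day cut should refer to being alive at Day 90, not at Visit 5, because Visit 5 may be as late as Day 97.

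The work is wording and programming, with no new data. The protocol edit would follow the amendment approvals in Protocol 8.1; if that is not wanted, the SAP edit alone settles what is reported.

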### 7.3.5 Pharmacokinetic and pharmacodynamic analyses

Not applicable.

## 7.4 INTERIM ANALYSES

An interim analysis will be performed when 60 patients enter and complete the study. All the first 60 patients who complete the study will be included in this interim analysis. Both safety and efficacy will be evaluated at interim analysis.

For efficacy, a predictive probability approach in the Bayesian setting is used to help to make the decision whether the study should continue to the full enrolment and whether an early application should be submitted to CFDA upon the promising interim results.

We target  $p_s = 55\%$  as a promising response rate in the end of study. The Bayesian analysis will be performed to estimate predictive probability (PP), which is the probability that the response rate reaches  $p_s$  or above in the final study result, given the data observed at interim time-point. If the predictive probability is greater than 90%, it shows the high potential of reaching promising result in the end given interim data.

In addition, we also consider a futile response rate lower than  $p_f = 40\%$  in the end of study for early stop at the interim. We estimate the predictive probability of observing the response rate lower than  $p_f$  in the end of study given interim data. If the predictive probability is greater than 90%, it shows high potential of futility in the end. [Appendix 10.5](#) elaborates how the predictive probability is calculated.

In summary, there are 3 scenarios suggested by the interim results as below,

- Scenario A - Early submission upon promising efficacy (i.e., promising zone): PP ( $\hat{p} \geq 55\%$ )  $\geq 90\%$ , equivalently, 37 or more responders among 60 patients at interim;
- Scenario B - Early stopping upon futile efficacy (i.e., Futility zone): PP ( $\hat{p} \leq 40\%$ )  $\geq 90\%$ , equivalently, 20 or fewer responders among 60 patients at interim;
- Scenario C - Competitive zone: the rest other than promising and futility zones;

For both scenarios A and C, if there is no safety alert from independent Data Monitoring Committee (DMC), the trial will continue for the completion of recruitment of 120 patients to the end as planned to collect the sufficient safety information.

In addition to the efficacy evaluation, an independent Data Monitoring Committee (DMC) will be constituted for continuously monitoring and reviewing the safety data during the study conduction. The details of the safety monitoring scheme will be specified in DMC SAP.

At the interim, it is envisioned that the DMC may make two types of recommendations, namely:

1. No safety issues or concerns, ethical to continue the trial as planned
2. Warning of significant safety concerns and recommendation of stopping the trial for patients' safety.

Table 7.4:1 Guidance for decision making at interim analysis

Timing and Results			Action
First 60 patients complete study			
Efficacy		Safety	
Promising Zone: $\geq 37$ patients with favourable outcome	AND	DMC declare no safety issues	Continue enrolment and early submission
Competitive Zone: $< 37$ but $> 20$ patients with favourable outcome	AND	DMC declare no safety issues	Continue enrolment without early submission
Futility Zone: $\leq 20$ patients with favourable outcome	OR	DMC declare warning of significant safety issues	early trial stopping

The guidance described in the Table 7.4.1 serves as decision base for early trial stopping or early submission to CFDA. The interim analysis in conjunction with other safety and efficacy data will be used to allow BI, in consultation with the investigators and DMC, to make a joint decision on whether the benefit and risk support continuation of the trial to the full enrolment up to 120 patients, and will help BI to make the decision on whether an early application should be submitted to CFDA.

The interim analysis will not lead to sample size recalculations and adjustment of enrolment targets.

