### **6.2.3      Observation Period and Trial Completion**

A physical examination, the documentation of adverse events and of concomitant medication will be performed for all patients at all predefined treatment time points (Visit 1B and Visit 1C) as of the administration day and visit 2,3,4, and 5.

Lab test at visit 1A and visit 3 are mandatory. It will be optional at visit 2 and visit 5 in case of clinical deterioration (considered by investigator)

At visit 1B (i.e., 1 hour after the start of infusion of study drug), vital signs will be measured every 30 minutes until Hour 2. An 12-lead ECG recording will be made.

At visit 1C (i.e., 2 hours after the start of infusion of study drug), the NIH Stroke Scale will be performed. Vital signs will be measured every 30 minutes for 6 hours, then hourly until 24 hours. An 12-lead An 12-lead ECG recording will be made.

At visit 2 (24 hours), vital signs will be measured. The NIH Stroke Scale will be performed. A second imaging (CT/MRI) scan will be done within Hour 22 and Hour 36 after start of infusion of study drug.

At visit 3 (on day 7), vital signs will be measured. The NIH Stroke Scale will be performed. An 12-lead ECG recording will be made. A CT/MRI scan will be performed in case of clinical deterioration

At visit 4 (on day 30), vital sign will be measured. The NIH Stroke Scale, the modified Rankin Scale, and the Barthel Index will be performed. A CT/MRI scan will be performed in case of clinical deterioration.

At visit 5 (on day 90), vital sign will be measured. The NIH Stroke Scale, the Glasgow Outcome Score, the modified Rankin Scale, and the Barthel Index will be performed. A physical examination takes place. The patient termination record will be filled in. Length of stay in hospital will be assessed as well.

The trial completion (end of the trial) eCRF page has to be filled-in when patient has terminated the trial.

The end of the trial is:

- At the end of visit 5(Day 90 per protocol) for patients who have completed the trial on treatment and came to future visits as planned.
- After early discontinuation, if a patient refuses to attend future visits as originally planned.

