### **7.3 PLANNED ANALYSES**

All enrolled patients who received Actilyse treatment at any dose will be included in the treated set (TS). This is also the full analysis set (FAS) since all treated patients will be evaluated. The primary efficacy analysis and the safety analysis will be performed on the TS.

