## **7.5 HANDLING OF MISSING DATA**

Every effort will be made to collect complete information according to the protocol. No missing values regarding vital status and intracranial bleeds are expected. However, for functional outcome parameters of surviving patients missing values might occur. The last observation carried forward (LOCF) method will be applied in the sense that data from the previous visit or measurement will substitute the missing data. In case of missing values due to death, the worst score principle will be applied.

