3. INTRODUCTION

As per ICH E9 [\[1\]](#), the purpose of this document is to provide a more technical and detailed elaboration of the principal features of the analysis described in the protocol, and to include detailed procedures for executing the statistical analysis of the primary and secondary variables and other data.

This trial statistical analysis plan (TSAP) assumes familiarity with the Clinical Trial Protocol (CTP), including Protocol Amendments. In particular, the TSAP is based on the planned analysis specification as written in Section 7 of the CTP [\[2\]](#) “Statistical Methods and Determination of Sample Size”. Therefore, TSAP readers may consult the CTP for more background information on the study, e.g., on study objectives, study design and population, treatments, definition of measurements and variables, planning of sample size, randomisation.

This TSAP is also used as the interim TSAP. The interim analysis will be performed when 60 patients enter and complete the study. The safety and efficacy will be evaluated on the first 60 patients who complete the study.

SAS® Version 9.2 versions will be used for all analyses.

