6.3 PATIENT SETS ANALYSED

The treated set (TS) includes all enrolled patients who received alteplase (rt-PA) treatment at any dose. The full analysis set (FAS) is the same as TS since all treated patients will be evaluated.

All safety and efficacy analysis will be performed on the TS.

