The length of stay in hospital is expressed in days and is equal to the date of discharge date and time is approximated to 23h O'clock for the end of day minus the date and time of the start of bolus. Because the date in SAS are expressed in seconds, the results will be divided by 86400 (24*60*60) in order to obtain a results expressed in number of days. The exact time of day of when the discharge time occurred is fixed at 23H59 PM for all patients (exact time not recorded in CRF).

Example: Start of bolus: 23/01/03 12H00 and date of discharge: 30/01/03

The length of stay in hospital will be: date of discharge (30/01/03, 23H59) - date of bolus (23/01/03, 12H00) / 86400 = 7.5 days.

Missing or incomplete AE onset dates are imputed according to BI standards [27, 27].

Missing or incomplete concomitant therapy onset dates are also imputed referring to AE standards. The end dates of missing or incomplete AE and concomitant therapy will be not imputed.

Trial completion is defined as the patients who are treated and completed Day 90 visit (i.e. Visit 5).

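### The interim set is the first 60 completers; read as written it omits deaths before Day 90 and makes the 37 and 20 cut-offs too lenient

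*Protocol*

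**What the plan says.** **Interim set.** Protocol 7.4: "All the first 60 patients who complete the study will be included in this interim analysis". SAP 3, which also serves as the interim SAP, agrees: "The safety and efficacy will be evaluated on the first 60 patients who complete the study". Table 7.4:1 uses the same trigger.

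**Completion.** SAP 6.6: "Trial completion is defined as the patients who are treated and completed Day 90 visit (i.e. Visit 5". Protocol 6.2.3 gives two routes to a patient's end of trial. One is Visit 5. The other is: "After early discontinuation, if a patient refuses to attend future visits as originally planned". Death is neither.

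**Analysis set and deaths.** Protocol 7.3: "The primary efficacy analysis and the safety analysis will be performed on the TS". SAP 6.3: "All safety and efficacy analysis will be performed on the TS". Protocol 7.5: "In case of missing values due to death, the worst score principle will be applied". SAP 6.6 makes that mRS 6, and Protocol 5.2 classes mRS 2 to 6 as unfavourable.

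**Use of the result.** Protocol 7.4 sets the promising zone at 37 or more responders out of 60 and the futility zone at 20 or fewer. Each is described as equivalent to a predictive probability of at least 90%. It adds: "The guidance described in the Table 7.4.1 serves as decision base for early trial stopping or early submission to CFDA".

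**The concern.** The two sets of rules cannot both hold for a patient who dies before Day 90. The treated-set and worst-score rules count that patient as a non-responder. The completer rule never admits the patient, and imputation cannot repair this because it acts only on patients already in the set.

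On the completer rule the bias has one direction. Only non-responders are lost to death, so the observed rate among the 60 exceeds the treated-set rate that the final analysis will estimate. The promising zone becomes easier to reach, and the futility zone harder to reach, than the 90% predictive probability implies. The decisions exposed are the early submission to the authority and the stop for futility.

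**Working it through.** **Inputs.** N = 120. The promising target is a final rate of at least 55%, i.e. 66/120. Futility is a final rate of at most 40%, i.e. 48/120. The interim is at 60 patients (all Protocol 7.4). The appendix describing the calculation is not in the public text, so a uniform Beta(1,1) prior is assumed. No planning death rate is given. The registry figure of 4.3% in Protocol 1.1 (no follow-up period stated) is used as an assumption, with 2% to 6% as the range.

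**Step 1: reproduce the plan's cut-offs.** With x responders among n patients whose outcome is known, responders among the remaining 120 − n follow a beta-binomial with parameters 1 + x and 1 + n − x. The predictive probability (PP) is P(x + future ≥ 66) for promising and P(x + future ≤ 48) for futility.

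- Promising: 36/60 gives 0.881 and 37/60 gives 0.939, so the cut-off is 37.
- Futility: 20/60 gives 0.940 and 21/60 gives 0.882, so the cut-off is 20.

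Both agree with the protocol. Beta(0.5,0.5) and Beta(5,5) priors give the same cut-offs. The calculation treats the 60 as an unselected half of the 120.

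**Step 2: put the omitted deaths back.** If k deaths were passed over while 60 completers accrued, 60 + k treated patients have a known outcome and 60 − k remain.

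| Deaths omitted (k) | PP promising, 37 responders | PP futility, 21 responders |
|---|---|---|
| 0 | 0.939 | 0.882 |
| 1 | 0.911 | 0.909 |
| 2 | 0.874 | 0.932 |
| 3 | 0.828 | 0.949 |

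From two omitted deaths, 37 responders no longer meet the 90% bar; 38 are needed (38/62 gives 0.935, 38/63 gives 0.906). From one omitted death, 21 responders already meet the futility bar although the table says continue. The count of 22 still does not with three (22/63 gives 0.898). With two or three omitted deaths, each boundary is therefore off by one responder. With two omitted deaths the other two priors agree: 37/62 gives 0.877 and 0.855, and 21/62 gives 0.935 and 0.907.

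**Step 3: how many deaths would be omitted.** Deaths before the 60th completer are negative binomial. At d = 0.043:

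- mean = 60 × 0.043/0.957 = 2.70
- P(at least 1) = 1 − 0.957^60 = 0.928
- P(at least 2) = 1 − 0.957^60 × (1 + 60 × 0.043) = 0.744

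**Step 4: effect on the zone probabilities.** If p is the treated-set response rate and d the death rate before Day 90, the completer response rate is p/(1 − d). For example, 0.50/0.957 = 0.522. Exact binomial tails with n = 60:

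| Quantity | No deaths omitted | d = 4.3% | d = 2% to 6% |
|---|---|---|---|
| P(≥37) at p = 50% | 4.6% | 9.1% | 6.4% to 11.7% |
| P(≥37) at p = 55% | 18.2% | 30.1% | 23.2% to 36.0% |
| P(≤20) at p = 35% | 45.2% | 35.3% | 40.6% to 31.5% |

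Only deaths are modelled. Patients lost alive are left out, because carrying the last observation forward may make some of them responders.

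**The case against.** **The sponsor may have meant deaths to count.** The SAP applies to the interim, so its treated-set and mRS 6 rules apply there too, and its survival and fatal-event outputs would be nearly empty in a survivors-only set. The completion sentence in SAP 6.6 follows date-handling rules and is not tied to the interim. Protocol 6.2.3 also has the completion form filled in once a patient has terminated the trial, a wider use of the term, and its two routes do not cover loss to follow-up either, so the list may not be exhaustive. This makes the inclusive intention plausible. It does not make it the rule: no visible text counts a death towards the 60. The appendix on predictive probability and the monitoring committee's own analysis plan are not available here and might say more.

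**The direction depends on the reading.** If a death counts as completed when it happens and patients are ordered by completion date, early deaths enter ahead of survivors still waiting for Day 90, and the bias reverses. That is correct, and it means neither completion-based reading gives the unselected 60 that the cut-offs need.

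**The consequence is limited.** The promising and middle zones both continue to 120 patients, the table is guidance used with other data, and the monitoring committee reviews safety separately and monthly. One omitted death leaves 37 valid. The change at 55% is not a wrong decision, since 55% is the plan's own target; the change at 50% is the more telling one. All of this stands and limits the importance of the point.

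**Conclusion.** The concern holds and should be fixed. As written, the interim set leaves out deaths before Day 90, contrary to the plan's treated-set and worst-score rules, and the 37 and 20 cut-offs then no longer correspond to 90% predictive probability. The error is about one responder at each boundary for two or three omitted deaths. At a true rate of 50% it roughly doubles the chance of the promising zone; at 35% it cuts the chance of a futility stop by about ten percentage points (45.2 − 35.3 = 9.9).

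These sizes rest on the literal reading, a uniform prior (the two-death conclusion also holds under the two other priors tried) and a death rate that is assumed, not planned. Confidence is medium because the intended reading is uncertain. The final treated-set analysis, its significance level and its power are not affected.

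**What to change.** In Protocol 7.4 (text and Table 7.4:1) and SAP 3, define the interim set as the first 60 consecutively treated patients. Run the analysis when each of them has a Day 90 mRS, has died (scored mRS 6), or has passed the Visit 5 window (83 to 97 days). Apply the SAP 6.6 imputation rules, use the same 60 patients for the interim safety tables, and keep the 37 and 20 cut-offs, which are correct for that set. Ordering by treatment removes the selection under either reading of completion.

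The change is to wording and needs no extra patients or data. The protocol part goes through the amendment approvals in Protocol 8.1. The interim rate may look slightly less favourable than it would among completers.
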